4.2.1.2.6 Medically-Attended Adverse Event

An event will be considered as an MAAE if "Yes" is checked for "Is the event an MAAE?" in the CRF. MAAE will be analyzed within 28 days after each vaccination, from D29 to 180 days after each vaccination, and within 180 days after each vaccination.

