8.3.1 Time Period and Frequency for Collecting AE and SAE Information

Immediate Post-vaccination Observation Period

Participants will be kept under observation for 30 minutes after each vaccination to ensure their safety. The post-vaccination observation should be documented in the source document.

Reactogenicity

Solicited injection site reactions will be collected for 7 days after each.

Solicited systemic reactions will be collected for 7 days after each vaccination.

The solicited injection site reactions and systemic reactions that are pre-listed in the diary cards and CRF, together with the intensity scales, are presented in Appendix 10.2.5.1.1.

Reactogenicity is to be reported only for IMPs. Refer to Table 6.1 to know which study intervention are considered as IMPs.

Unsolicited Non-serious Adverse Events

Unsolicited non-serious adverse events will be collected for 28 days after each.

The intensity grading scale for unsolicited non-serious adverse events is presented in Appendix 10.2.5.1.2.

Medically Attended Adverse Events (MAAEs)

MAAEs will be collected for 28 days after each vaccination.

Adverse Events of Special Interest (AESIs)

AESIs will be collected at any time during the study.

See Section 8.3.6 for the list of AESIs.

SAEs

Information on SAEs will be collected and assessed throughout the study, from the first dose until 6 months after the last vaccination. However, before the first study intervention administration,

only SAEs related to study procedures are to be collected in the case report form (CRF) (eg, SAEs related to blood sampling).

All SAEs will be recorded and reported to the Sponsor or designee immediately and under no circumstance should this exceed 24 hours, as indicated in Appendix 10.2. The investigator will submit any updated SAE data to the Sponsor within 24 hours of it being available.

Investigators are not obligated to actively seek information on AEs or SAEs after conclusion of the study participation. However, if the investigator learns of any SAE, including a death, at any time after a participant has been discharged from the study, and he/she considers the event to be reasonably related to the study intervention or study participation, the investigator must promptly notify the Sponsor.

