8.3.2 Method of Detecting AEs and SAEs

Individual diary card/electronic diary cards, specifically designed for this study by the Sponsor and provided to the study sites, will be given to study parents / legally acceptable representatives for the recording of daily safety information. These diary cards will include pre-listed terms and intensity scales as well as areas for free text to capture additional safety information or other relevant details. Parents / legally acceptable representatives will also be provided with rulers for measuring the size of injection site reactions, and with standard digital thermometers for measuring daily temperatures. To ensure consistency of reporting, the study sites will instruct parents / legally acceptable representatives on how to correctly use these tools.

At specified intervals, the Investigator or a designee will interview the parents / legally acceptable representatives to collect the information recorded in the diary card/electronic diary card, and will attempt to clarify anything that is incomplete or unclear. All clinical study information gathered by the study site will be reported electronically by the Investigator or designee using a web-based CRF. Any information that was not documented in the diary card/electronic diary card will first be captured in the source document and then reported electronically.

The 6-month follow-up will be done by interviewing parents / legally acceptable representatives either during a visit or over the telephone using a questionnaire to capture SAEs and AESIs, if applicable.

Care will be taken not to introduce bias when detecting AEs and/or SAEs. Open-ended and non-leading verbal questioning of the participant's parent(s)/legally acceptable representative is the preferred method to inquire about AE occurrences.

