• To demonstrate the non-inferior hemagglutination inhibition (HAI) immune response of RIV4 vs licensed IIV4 for the 4 strains based on the egg-derived antigen in all participants aged 3 to 8 years	 Individual HAI titer 28 days after the last vaccination (D29 or D57¹) Seroconversion (SC) (titer < 10 [1/dil] at D01 and post-injection titer ≥ 40 [1/dil] at D29 or D57, or titer ≥ 10 [1/dil] at D01 and a ≥ 4-fold-rise in titer [1/dil] at D29 or D57)
Secondary	
 Immunogenicity To summarize the HAI immune response induced by RIV4 and IIV4 for the 4 strains based on the egg-derived antigen in participants aged 3 to 8 years 	 Individual HAI titer on D01 and 28 days after the last vaccination (D29 or D57) Detectable HAI titer, ie, with a titer ≥ 10 (1/dil) at D01 and 28 days after the last vaccination (D29 or D57) Individual HAI titer ratio: 28 days after the last vaccination (D29 or D57) / D01 Seroconversion (titer < 10 [1/dil] at D01 and post-injection titer ≥ 40 [1/dil] at D29 or D57, or titer ≥ 10 [1/dil] at D01 and a ≥ 4-fold rise in titer [1/dil] at D29 or D57) Participants with titers ≥ 40 (1/dil) on D01 and 28 days after the last vaccination (D29 or D57)
 Safety To assess the safety profile of each vaccine in all participants and by age group 	 Occurrence of any unsolicited systemic adverse events (AEs) reported in the 30 minutes after each vaccination Occurrence of solicited (pre-listed in the participant's diary card [DC]/electronic DC [eDC] and case report book [CRB]) injection site reactions and systemic reactions occurring up to 8 days after each vaccination

¹ Depending on vaccination schedule/influenza previous vaccination: 1 dose received during the study = D29 and 2 doses received during the study = D57

Confidential/Proprietary Information Page 13 of 40

	Objectives		Endpoints
		•	Occurrence of unsolicited AEs up to 28 days after each vaccination
		٠	Occurrence of medically attended adverse event (MAAEs) up to 28 days after each vaccination
		•	Occurrence of serious adverse events (SAEs) (including adverse events of special interest [AESIs]) throughout the study
		•	Occurrence of AESIs throughout the study
	Exploratory		
•	To describe the neutralizing antibody immune response based on the egg-derived antigen in a	•	Individual seroneutralization (SN) antibody (Ab) titer on D01 and 28 days after the last vaccination (D29 or D57)

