For solicited reactions, the denominator will be the total number of participants who have nonmissing data for the endpoint considered.

For unsolicited AEs, the denominator will be the total number of participants who were vaccinated.

In terms of contents, solicited reactions will be presented by time to onset, maximum severity, number of days of occurrence and action taken; unsolicited AEs will be presented by causal relationship, time of onset, maximum severity and duration; SAEs will be presented by causal relationship, seriousness and outcome.

Subgroup analyses will also be performed; in particular, the main safety endpoints will be described according to age subgroups (3 to 5 and 6 to 8 years), previous vaccination status, sex and race, as appropriate according to number of participants in the respective subgroups.

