4.2.1.2.3 Last Vaccination

Last vaccination before an unsolicited AE will be derived from the pre-visit numbers provided in the clinical database and will be calculated as follows:

- If an unsolicited AE has a non-missing pre-visit number, the pre-visit number will be used to determine the last vaccination before the unsolicited AE
- If the pre-visit number is missing and the start date is complete (ie, including day), then the start date will be used to determine the last vaccination before the unsolicited AE
- If an unsolicited AE has a missing pre-visit number and a partial start date (at least day missing), the unsolicited AE will be considered as post injection 1.

Confidential/Proprietary Information Page 32 of 40

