4.2.1.2.4 Time of Onset

Time of onset is derived from the start date of the unsolicited AE and the date of vaccination:

Time of Onset = start date of the unsolicited AE - date of vaccination + 1 (if D01 is the first vaccination day).

The time of onset is considered as missing only if one or both dates are missing or partially missing.

The unsolicited AEs will be analyzed "Within 28 days" after each vaccination, which corresponds to AEs with a time of onset between D1 and D29 or missing. An AE with missing time of onset will be considered to have occurred just after the vaccination, so will be included in these tables.

Time of onset period is displayed as D01-D04, D05-D08, D09-D15, D16 or later, and Missing.

Note: Unsolicited AE that occurred before vaccination (negative time of onset) or with a time of onset higher than defined above will not be included in analysis but will be listed separately.

4.2.1.2.5 **Duration**

Duration is derived from the start and end dates of the unsolicited AE:

• Duration = End date of unsolicited AE - start date of unsolicited AE + 1.

The duration is considered as missing only if one or both of the start and end dates of the unsolicited AE is missing or partially missing.

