4.2.1.2.7 Serious Adverse Events

An event will be considered as a serious event if "Yes" is checked for "Serious" in the CRF.

SAEs will be analyzed within 28 days after each vaccination, from D29 to 180 days after each vaccination, and within 180 days after each vaccination.

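### The SAP plans 180-day tables of medically attended adverse events, but those events are collected for only 28 days after each dose

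*SAP*

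**What the plan says.** SAP 4.2.1.2.6 sets three analysis periods for MAAEs. The first two are given as "MAAE will be analyzed within 28 days after each vaccination, from D29 to 180 days after each vaccination", and the third is the whole 180 days after each dose. SAP 4.2.1.2.7 uses the same pattern for serious events ("SAEs will be analyzed within 28 days after each vaccination, from D29 to 180 days after each vaccination"), and 4.2.1.2.8 does so for AESIs.

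On collection, Protocol 8.3.1 says "MAAEs will be collected for 28 days after each vaccination". The MAAE endpoint in SAP Table 2.1 reads "Occurrence of medically attended adverse event (MAAEs) up to 28 days after each vaccination", matching Protocol Table 3.1 and the synopsis. The MAAE rows of Protocol Tables 1.1 and 1.2 and of SAP Tables 1.2 and 1.3 give the same 28 days. Protocol 8.3.2 describes the 6-month contact as "using a questionnaire to capture SAEs and AESIs, if applicable".

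Three analysis rules also bear on this. SAP 3.4.3 states: "For unsolicited AEs, the denominator will be the total number of participants who were vaccinated". SAP 4.2.1.2.3 states: "Last vaccination before an unsolicited AE will be derived from the pre-visit numbers provided in the clinical database". SAP 4.2.1.2.4 defines the 28-day period as one "which corresponds to AEs with a time of onset between D1 and D29 or missing"; its closing note sends unsolicited AEs with later onset to a listing and keeps them out of the analysis.

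**The concern.** Two of the three MAAE windows extend well beyond the period in which sites are asked to record MAAEs. The three-window wording suits SAEs and AESIs, which are collected throughout the study. It does not suit MAAEs.

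If the SAP is followed as written, the study report would show a 180-day MAAE percentage based on everyone vaccinated, with no allowance for the fact that collection stopped at 28 days. It would also show a nearly empty table for D29 to day 180. A reader could take that table as evidence of few late medically attended events in children, when nobody was systematically asked about them. The trial is meant to support extending the indication to children, so safety tables should not imply more follow-up than took place.

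A smaller point concerns the boundary. The 28-day period includes D29 and the late period starts at D29, so for MAAEs, SAEs and AESIs alike an event on that day belongs to both.

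**Working it through.** The plan gives no figure to reproduce. The check compares the windows and counts days.

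**Collection against analysis**

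| Event | Collected | Analysed | Match? |
|---|---|---|---|
| MAAE | 28 days post-dose (Protocol 8.3.1; Protocol Tables 1.1, 1.2, 3.1; SAP Tables 1.2, 1.3, 2.1) | 28 days; D29 to 180; 180 days (SAP 4.2.1.2.6) | First window only |
| SAE | To 6 months after the last dose (Protocol 8.3.1) | Same three windows (SAP 4.2.1.2.7) | Yes, apart from D29 |
| AESI | Throughout the study (Protocol 8.3.1) | Same three windows (SAP 4.2.1.2.8) | Yes, apart from D29 |

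No section extends MAAE collection. Protocol 8.3.7 ties it to the process for other AEs, and SAP section 5 records no such change.

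**Day counts.** SAP 4.2.1.2.4 numbers the vaccination day D1, so 180 days later is D181. Collection covers D1 to D29.

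*After the last dose* (one-dose child, or two-dose child counted from dose 2):
- 180-day window: 29 / 181 = 16.0% of onset days under collection.
- Late window D29 to D181: 181 − 29 + 1 = 153 days, of which 1 (D29) is covered: 1 / 153 = 0.7%.
- Late window starting at D30: 0 of 152 days.

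*Two-dose child counted from dose 1.* Collection after dose 2 adds days. The dose 2 visit window is −2 to +7 days around D29 (Protocol Table 1.2).

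| Dose 2 on | Days collected | 180-day window | Late window |
|---|---|---|---|
| D27 | D1–D55 | 55 / 181 = 30.4% | 27 / 153 = 17.6% |
| D29 | D1–D57 | 57 / 181 = 31.5% | 29 / 153 = 19.0% |
| D36 | D1–D29 and D36–D64 | 58 / 181 = 32.0% | 30 / 153 = 19.6% |

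This second case is an upper bound on coverage. SAP 4.2.1.2.3 attributes an event to the most recent dose before it, so events after dose 2 would normally count against dose 2 and the first set of figures applies.

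**What the late MAAE tables could contain.** There are three possible sources: events with onset on D29; late SAEs or AESIs that also have the MAAE box ticked in the CRF; and, only if counted from dose 1, events collected after dose 2. A non-serious MAAE with onset at, say, D40 after the last dose has no routine route into the database.

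**A conflict within the SAP.** The MAAE definition in Protocol 10.2.1 excludes solicited reactions, so MAAEs are unsolicited AEs. For one that is reported with onset at D40, the note in SAP 4.2.1.2.4 says list and do not analyse, while 4.2.1.2.6 says analyse.

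**The case against.** The strongest reply is about weight. The declared endpoint is the 28-day one, and it remains correctly defined and analysable. Safety is descriptive with no hypotheses tested, and the interim safety summaries stop at D29 after the last vaccination (SAP 3.5.1). The harm is a table that could be misread, and a clear label would also deal with that. All of this is right, and it limits the point to two descriptive outputs.

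The late window is also not strictly empty: late SAEs and AESIs flagged as MAAEs could legitimately appear. But those events are already reported under their own headings, and showing them as a 180-day MAAE rate leaves out the non-serious events.

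The note in SAP 4.2.1.2.4 already moves late unsolicited AEs to a listing, so part of the remedy exists. That supports the change but does not settle it. Read literally, the note would also exclude late SAEs, so the windows in 4.2.1.2.6 to 4.2.1.2.8 may be intended as exceptions to it.

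Finally, the day shares are shares of calendar time, not of events, and nothing says the D29-overlapping windows will be added together. Both points stand; the overlap is a wording correction.

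**Conclusion.** The inconsistency is real. The D29-to-180-day and 180-day MAAE analyses in SAP 4.2.1.2.6 have no matching collection period and contradict the protocol and the SAP's own schedules and endpoint table. After the last dose, 16% of the 180-day window and 1 day in 153 of the late window are under MAAE collection. These counts assume that the vaccination day is D1 and that collection stops at D29. The resulting understatement in event rates cannot be calculated, because the documents give no MAAE rate.

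The 28-day MAAE endpoint and the primary non-inferiority tests are unaffected. SAE and AESI analyses are touched only by the one-day overlap at D29. The SAP should be corrected before database lock.

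**What to change.** 1. In SAP 4.2.1.2.6, delete the two later windows. Analyse MAAEs only over the 28-day period as defined in 4.2.1.2.4 (onset D1 to D29, or missing).
2. Put any MAAE with later onset in a separate listing, labelled as not systematically collected. This follows the existing note in 4.2.1.2.4.
3. In SAP 4.2.1.2.7 and 4.2.1.2.8, keep the 180-day analyses but start the late window at D30.

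The cost is three edited SAP sentences, two fewer sets of MAAE tables and one listing label. Data collection does not change. Protocol 9.4 already provides for amending the SAP before any database lock. Making the longer MAAE windows meaningful would instead require a protocol change, and about 366 children had already been enrolled under the 28-day schedule by the interim analysis (SAP 3.5).

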4.2.1.2.7 Serious Adverse Events

An event will be considered as a serious event if "Yes" is checked for "Serious" in the CRF.

SAEs will be analyzed within 28 days after each vaccination, from D29 to 180 days after each vaccination, and within 180 days after each vaccination.

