2.3.3 Overall Benefit-Risk Conclusion

Considering the measures taken to minimize risk to participants enrolled in this study, the potential risks that may result from study participation are balanced by the anticipated benefits that may be afforded to participants.

3 Objectives and Endpoints

The study objectives and the corresponding endpoints are described in Table 3.1.

Table 3.1	Objectives	and endpoints
-----------	-------------------	---------------

	Objectives	Endpoints	
Priz	mary		
•	To demonstrate the non-inferior HAI immune response of RIV4 vs licensed IIV4 for the 4 strains based on the egg-derived antigen in all participants aged 3 to 8 years	 Individual HAI titer 28 days after the last vaccination (D29 or D57^a) Seroconversion (titer < 10 [1/dil] at D01 and post-injection titer ≥ 40 [1/dil] at D29 or D57, or titer ≥ 10 [1/dil] at D01 and a ≥ 4-fold-rise in titer [1/dil] at D29 or D57) 	

^a Depending on vaccination schedule/influenza previous vaccination: 1 dose received during the study = D29 and 2 doses received during the study = D57

Objectives		Endpoints	
	Secondary		
Im •	munogenicity To summarize the HAI immune response induced by RIV4 and IIV4 for the 4 strains based on the egg-derived antigen in participants aged 3 to 8 years	 Individual HAI titer on D01 and 28 days after the last vaccination (D29 or D57) Detectable HAI titer, ie, with a titer ≥ 10 (1/dil) at D01 and 28 days after the last vaccination (D29 or D57) Individual HAI titer ratio: 28 days after the last vaccination (D29 or D57) / D01 Seroconversion (titer < 10 [1/dil] at D01 and post-injection titer ≥ 40 [1/dil] at D29 or D57, or titer ≥ 10 [1/dil] at D01 and a ≥ 4-fold rise in titer [1/dil] at D29 or D57) Participants with titers ≥ 40 (1/dil) on D01 and 28 days after the last vaccination (D29 or D57) 	
Sa.	fety To assess the safety profile of each vaccine in all participants and by age group	 Occurrence of any unsolicited systemic adverse events reported in the 30 minutes after each vaccination Occurrence of solicited (pre-listed in the participant's diary card [DC]/electronic DC [eDC] and case report book [CRB]) injection site reactions and systemic reactions occurring up to 8 days after each vaccination Occurrence of unsolicited AEs up to 28 days after each vaccination Occurrence of medically attended adverse event (MAAEs) up to 28 days after each vaccination Occurrence of SAEs (including AESIs) throughout the study Occurrence of AESIs throughout the study 	

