8.3.6 Adverse Events of Special Interest

AESIs will be captured as SAEs. These include new onset of GBS, encephalitis/myelitis, including transverse myelitis, Bell's palsy, optic neuritis, brachial neuritis, thrombocytopenia, vasculitis, and anaphylaxis.

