4.2.1.2.8 Adverse Events of Special Interest

An event will be considered as an AESI if "Yes' is checked for "Is the event an AESI?" in the CRF.

AESIs will be analyzed within 28 days after each vaccination, from D29 to 180 days after each vaccination, and within 180 days after each vaccination.

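### SAP safety windows: D29 sits in both the early and the late SAE/AESI window, and no specified window runs past 180 days to a late last contact

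*SAP*

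**What the plan says.** **Endpoint.** Protocol Table 3.1 lists "Occurrence of SAEs (including AESIs) throughout the study" and has a separate line for AESIs; SAP Table 2.1 repeats both.

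**Collection.** Protocol 8.3.1 states: "Information on SAEs will be collected and assessed throughout the study, from the first dose until 6 months after the last vaccination". For AESIs the same section says "AESIs will be collected at any time during the study", and 8.3.6 adds that "AESIs will be captured as SAEs".

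**Last contact.** The schedules of activities (Protocol Tables 1.1 and 1.2) place the final call 180 days after the only or second vaccination, nominally D181 or D209. The window is one-sided, allowing up to 14 days late and none early.

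**Analysis windows.** SAP 4.2.1.2.7 analyses SAEs within 28 days of each vaccination, then "from D29 to 180 days after each vaccination, and within 180 days after each vaccination". SAP 4.2.1.2.8 uses the same windows: "AESIs will be analyzed within 28 days after each vaccination, from D29 to 180 days after each vaccination", plus a 180-day total. SAP 4.2.1.2.6 applies them to MAAEs as well.

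**Day numbering.** SAP 4.2.1.2.4 computes onset as start date minus vaccination date plus 1. It says that the 28-day analysis "corresponds to AEs with a time of onset between D1 and D29 or missing". A note there adds that unsolicited AEs "with a time of onset higher than defined above will not be included in analysis but will be listed separately".

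**The concern.** There are two separate points.

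First, the early window ends on D29 and the late window begins on D29. They share a day, so the rule does not say to which period a D29 event belongs. D29 is not an arbitrary day: it is the nominal day of Visit 2 and, in the two-dose schedule, of the second injection.

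Second, the endpoint and the AESI collection rule run through the whole study, while the longest specified window stops at 180 days. Because the final call can be late but not early, any delay adds observed time after the cut-off. The SAP's own participant duration (4.2.4.3) runs to the actual safety follow-up date, so that time counts as participation. The AESI list in Protocol 8.3.6 includes Guillain-Barré syndrome and encephalitis/myelitis, for which a single case changes what is reported. A Guillain-Barré onset on D185 in a one-dose child, recorded at an in-window call, would meet the endpoint but fall in none of the specified windows.

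**Working it through.** **1. Reproduce the plan's day labels.** With onset day = days after vaccination + 1:
- 28 days after vaccination: 28 + 1 = D29, as SAP 4.2.1.2.4 states.
- 180 days after a single dose: 180 + 1 = D181, as in Protocol Table 1.1.
- 180 days after a second dose given on D29: 29 + 180 = D209, as in Protocol Table 1.2.

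**2. Overlap.**
- Early window D1 to D29: 29 days.
- Late window D29 to D181: 181 − 29 + 1 = 153 days.
- Sum: 29 + 153 = 182 window-days for 181 actual days, so exactly one day (D29) is shared.
- The 180-day window, D1 to D181, is defined separately and contains D29 once.

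**3. Effect of starting the late window at D30.** D30 to D181 is 152 days, and 29 + 152 = 181. The two windows no longer overlap and together equal the 180-day window.

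**4. Tail after 180 days.**
- One dose: the latest in-window call is D181 + 14 = D195. The uncovered share is at most 14/195 = 7.2%.
- Two doses, dose 2 on D29: the latest call is D209 + 14 = D223. The share is at most 14/223 = 6.3%.
- Across the permitted Visit 2 window (D27 to D36), the latest call falls between D221 and D230, giving 14/221 = 6.3% to 14/230 = 6.1%.
- A call made on the planned day leaves no tail.

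**5. Expected counts (assumption).** The documents give no SAE rate. Suppose 0.5% to 2% of the 1412 children have one SAE in 180 days at a constant rate, that is 7.06 to 28.24 events.
- Tail if every call is 14 days late: 7.06 × 14/180 = 0.5 to 28.24 × 14/180 = 2.2 SAEs.
- Tail if calls average 7 days late: half of that, 0.3 to 1.1 SAEs.
- Onset on D29: 7.06/180 = 0.04 to 28.24/180 = 0.16 SAEs.

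**6. MAAEs.** Protocol 8.3.1 collects MAAEs for 28 days after each vaccination. The two windows in SAP 4.2.1.2.6 that run to 180 days therefore have no planned MAAE collection after day 28.

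**The case against.** A reader might infer that the tables do not estimate the stated endpoint. The documents do not support that. Protocol 8.3.1 itself describes SAE collection as running to six months after the last vaccination. The 180-day window, counted from each dose, reaches the planned last contact in both schedules. The D29 overlap cannot support that reading either, because it touches only the split into sub-windows.

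A reader might also infer that every D29 event after dose 1 in two-dose children is counted twice. SAP 4.2.1.2.3 assigns each unsolicited AE to its last vaccination, by pre-visit number or else by complete start date, and Protocol 10.2.1 counts SAEs among unsolicited AEs. An event assigned to dose 2 on that day is D1 of dose 2. The overlap applies only when the event is assigned to the dose for which it is D29. Nor should the sub-windows be expected to sum to the total in participant counts: a child with events in both periods breaks that sum even with clean boundaries.

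A third inference is that SAEs after day 180 are certainly relegated to a listing. The note in SAP 4.2.1.2.4 was written for the 28-day analysis, and the only upper limit defined above it is D29. Applied literally to SAEs it would remove the whole late period, which 4.2.1.2.7 contradicts. SAP 3.4.3 describes the SAE presentation without a time limit, and the safety analysis set allows an analysis after any dose. So the plan leaves the handling of such events unstated; it does not establish that they are lost.

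One could also read the second D29 as 29 days after vaccination, which would remove the overlap. SAP 3.5.1 and 3.5.2.4 use D29 after the last vaccination as the 28-day timepoint, so that reading is strained. Finally, a fixed 180-day window gives children a common planned observation period, a real merit and the reason to keep that table.

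What remains is the one-day overlap and the absence of any specified window reaching a late last contact.

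**Conclusion.** The point holds in this limited form and is minor. Under the SAP's own numbering, D29 of a given dose belongs to both SAE/AESI sub-windows; the 180-day total is unaffected. That total covers planned follow-up, but nothing specified covers the interval from day 180 to a late in-window call. The percentages in the working are ceilings, reached only by a child called on the last permitted day. The event counts rest on an assumed SAE frequency and constant hazard, and serve only to show the scale. All safety analyses are descriptive (SAP 3.4.3), so no hypothesis test or primary result changes. The practical reason to act is that one rare AESI in the tail could be left out of every specified window.

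**What to change.** - In SAP 4.2.1.2.7 and 4.2.1.2.8, start the late window at D30 (29 days after vaccination).
- Add one SAE/AESI summary from first dose to last contact and name it as the table for the whole-study endpoint. Keep the 180-day table beside it.
- In SAP 4.2.1.2.6, either apply the same boundary or delete the MAAE windows beyond 28 days, in line with the protocol's collection period.

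The cost is SAP wording and one extra table column; data collection and trial conduct do not change. One small drawback is that, among children called within the window, post-vaccination observation in the added summary varies by up to 14 days. A footnote can say so.
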